### 10.2 Secondary study parameter(s)

The secondary research aim is to investigate whether there are differences between severe periodontitis and mild/moderate periodontitis. As such, mild/moderate periodontitis will be labelled as "control" while severe periodontitis patients are labelled as "cases". In secondary analyses exact procedures are followed as described above for the primary outcomes.

### **10.3 Other study parameters**

Other study parameters that will be obtained and used as covariates are sex (M/F), age (years), ethnicity (origin of parents) (Europe/Non-Europe), education level (high/low), smoking habits (yes/no), diagnosis of hypertension (yes/no), diagnosis of ASCVD (yes/no), medical treatment for ASCVD (yes/no), relatives with ASCVD (yes/no), diagnosis of hypercholesterolemia (yes/no), medical treatment for hypercholesterolemia (yes/no), diagnosis of DM (yes/no), relatives with DM (yes/no), history of periodontal treatment (yes/no), height (cm) and body weight (kg) (for determining the BMI), neck and waist circumference (cm), blood pressure (mmHg), physical activity (Metabolic Equivalent of Task).

**10.4 Interim analysis (if applicable)** NA

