### 4.4 Sample size calculation

The calculation of the sample size was based on a  $Chi^2$ -test having an  $\alpha$ <0.05 with 90% power and using the prevalence of diabetes of two groups (without periodontitis: 8.5%, severe periodontitis: 18.1%)(13). The required sample size is a minimum of 261 subjects per group.

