### NL62337.029.17 / ParoSysACTA Periodontitis as signal for an underlying disease

### **10. STATISTICAL ANALYSIS**

The prevalence of (pre)DM and MetS, the 10-year risk of ASCVD and the risk of OSAS will be presented in tables. First, one table will be generated describing the background variables, blood chemistry and demographic characteristics. Secondly, the prevalence of (pre)DM and MetS, the 10-year-risk of CVD and the OSAS risk will be reported in patients with and without periodontitis.

According to the ADA guidelines HbA1c values will be classified as normal (<5.7% [<39 mmol/mol]), preDM (5.7-6.4% [39-47 mmol/mol]) and DM (≥6.5% [≥48 mmol/mol]) (7).

The 10-year risk of ASCVD will be assessed with help of the risk table from the Dutch guideline on cardiovascular risk management (CVRM) according to the standards of the Dutch College of General Practitioners (NHG) (20). The NHG standards are derived from European Society of Cardiology guidelines and modified to the Dutch situation (6).

According to the NCEP ATP III guidelines MetS is present if three of the 3 or more of the five criteria are met: elevated waist circumference over  $\geq$  102 cm (men) or  $\geq$  88 cm (women), triglyceride (TG) level over  $\geq$  1.7 mmol/L or being on drug treatment for elevated TG, high density lipoprotein cholesterol (HDL-C) level less than < 1.03 mmol/L (men) or < 1.3 mmol/L (women), blood pressure over 130/85 mmHg or on antihypertensive drug treatment, and blood glucose level over  $\geq$  5/6 mmol/L (21).

The OSAS risk is calculated with help of a new questionnaire (PhilipsQ) which is constructed from body measurements (sex, age, BMI, neck circumference) and the most predictive questions of the following OSAS and sleep questionnaires: Berlin Questionnaire (BerlinQ), STOP Questionnaire (STOPQ) and Athens Insomnia Scale (AIS). An algorithm is developed to compute the individual estimated probability (p) that a subject will have OSAS: p(OSAS) = 1 / (1+e-X), where  $X = -6.322 + 2.828 \times AIS + 2.745 \times STOPBANGQ$  High + 0.965 × STOPBANGQ Intermediate + 4.640 × BerlinQ High + 1.584 × BerlinQ Intermediate + 0.790 × Age + 0.810 × BerlinQ Q-5. The final cutoff values were determined by exploratory logistic regression analyzes. The risk of OSAS will be classified as low (p[OSAS] < 35%), intermediate (p[OSAS] = 35-55%) and high (p[OSAS] > 55%) (22).

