The missing data from included subjects will be imputed using the expectationmaximization method. Background variables, blood chemistry and demographic data between cases and controls will be analysed by Chi-analyses or t-tests where applicable. The primary and secondary outcome variables will be analysed both by univariate analysis and multivariate analysis (multiple logistic regression). The data will be analysed on an intention-to-treat basis (ITT).

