### **10.1 Primary study parameter(s)**

The cases and controls are a priori defined by inclusion and exclusion criteria. The STROBE guideline will be followed and a flow diagram will be generated of how many individuals have been screened, invited to participate, included and analysed (29). All initially included study subjects will form part of the data analysis (intention to treat). Type I error will be controlled by including a sufficient number of cases and controls to avoid multiplicities and to apply Bonferroni corrections where applicable. Secondly, we have determined the minimal sample size on the basis of an appropriate power calculation (see chapter 4.4).

The prevalence of (pre)diabetes, the 10-year risk of ASCVD, the prevalence of MetS and the prevalences of OSAS risks (categorical variables) within the study population will be compared with parametric and non-parametric tests (ANOVA and  $Chi^2$ -test). Where applicable, analyses will be corrected for multiple testing (Bonferroni). The significance level will be set to p<0.05.

The prevalence of (pre)DM among cases and controls will be firstly reported without adjustment of any of potential covariates. In a second exploratory analysis we will adjust the prevalence for general and diabetes and ASCVD related characteristics of the study population: sex, age, ethnicity (origin of parents), education level, smoking habits, relatives with DM, history of periodontal treatment, diagnosis of hypertension, diagnosis of hypercholesterolemia, diagnosis of DM and the BMI, amount of physical activity.

The 10-year risk of ASCVD will be calculated according to the algorithm from the ESC guidelines, which is adapted to the Dutch situation. No further adjustments will be done.

The prevalence MetS will be calculated according to the criteria of the NCEP ATP III guidelines. No covariates will be included.

The risk for OSAS will be assessed by the OSAS questionnaire. No further adjustments will be done. However, the results will be explored in relation to having periodontitis, the

background characteristics, the blood chemistry outcomes and having (pre)diabetes and the 10-year risk for ASCVD.

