# APPENDIX 4: Criteria for diagnosis of Metabolic Syndrome (MetS) according to the NCEP ATP III (21)

Measure (any 3 of 5 constitute	Categorical cutpoints
diagnosis of metabolic syndrome)	
Elevated waist circumference (WC)	$\geq$ 102 cm in men
	$\geq$ 88 cm in women
Elevated triglycerides (TG)	$\geq$ 1.7 mmol/L
	or
	On drug treatment for elevated TG
Reduced HDL-C	< 1.03 mmol/L in men
	< 1.3 mmol/L in women
	or
	On drug treatment for reduced HDL-C
Elevated blood pressure	≥ 130 mmHg systolic blood pressure
	or
	≥ 85 mmHg diastolic blood pressure
	or
	On antihypertensive drug treatment in a
	patient with a history of hypertension
Elevated fasting glucose	$\geq$ 5.6 mmol/L

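### Sections 10 and 10.3 call for models that adjust outcomes for their own components, section 10.1 largely says not to adjust, and no precedence is stated

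*Combined protocol and SAP*

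**What the plan says.** Three parts of the combined protocol and SAP bear on which variables enter an adjusted model.

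- **Section 10, opening text:** "The primary and secondary outcome variables will be analysed both by univariate analysis and multivariate analysis (multiple logistic regression"). No outcome is exempted.
- **Section 10.3:** "Other study parameters that will be obtained and used as covariates are sex (M/F), age (years"), followed by a long list ending in height and weight for BMI, then "neck and waist circumference (cm), blood pressure (mmHg), physical activity (Metabolic Equivalent of Task"). The list is pooled. No item is tied to an outcome or model.
- **Section 10.1:** for (pre)DM, an unadjusted report comes first, then an exploratory analysis adjusted for 12 named items. These exclude waist, neck and measured blood pressure but include a prior diagnosis of DM. For MetS the section rules out covariates. For ASCVD risk and OSAS risk it says that nothing further is adjusted for, although the OSAS results are then to be explored against periodontitis, background characteristics and blood chemistry.

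Section 10.2 applies the same procedures to severe versus mild/moderate periodontitis.

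Several 10.3 variables are also outcome inputs. Appendix 4 makes "Elevated waist circumference (WC") and elevated blood pressure two of the five MetS criteria. Systolic pressure is an axis of the Appendix 3 risk chart. The OSAS questionnaire is described in section 10 as "constructed from body measurements (sex, age, BMI, neck circumference") together with items from sleep questionnaires.

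**The concern.** An analyst who obeys sections 10 and 10.3 fits a MetS model with waist and blood pressure on the right-hand side. The periodontitis coefficient then answers whether periodontitis patients have more MetS at the same waist and blood pressure. Section 2 asks something else: whether prevalence differs between the groups. The same applies to blood pressure in an ASCVD-risk model and to neck circumference and BMI in an OSAS model.

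An analyst who obeys section 10.1 fits no adjusted MetS model at all. Both have followed the plan. The adjusted results for three of the four main outcomes are therefore open to a choice made after the data are seen, and one of the available choices is circular.

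**Working it through.** **1. The plan's own figure.** Section 4.4 sizes the study "with 90% power and using the prevalence of diabetes of two groups" ("without periodontitis: 8.5%, severe periodontitis: 18.1"%), and section 10.1 states "The significance level will be set to p<0.05". Taking the test as two-sided, with pooled variance under the null:

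n = [1.960·√(2·0.133·0.867) + 1.2816·√(0.085·0.915 + 0.181·0.819)]² / 0.096² = (0.941 + 0.609)² / 0.009216 ≈ 260.9, so 261 per group.

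The figure reproduces. It concerns an unadjusted DM comparison, so it neither supports nor contradicts any adjusted model. It is used below only for group sizes.

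**2. The texts side by side.**

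| Outcome | Section 10 opening | Section 10.1 | Own inputs found in the 10.3 list |
|---|---|---|---|
| (pre)DM | logistic model | 12 listed items, exploratory | prior DM diagnosis (also in the 10.1 list) |
| ASCVD risk | logistic model | nothing further adjusted | blood pressure, age, sex, smoking, DM diagnosis |
| MetS | logistic model | no covariates | waist, blood pressure, hypertension diagnosis (through the treated-hypertension limb of the criterion) |
| OSAS risk | logistic model | nothing further adjusted, but explored | neck circumference, BMI, age, sex |

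For MetS the conflict is direct. For ASCVD and OSAS the 10.1 sentence follows one on how the score is obtained, so it could refer to the score or to the group comparison. If 10.1 governs throughout, waist, neck and measured blood pressure are covariates in no specified model, and 10.3 is still wrong as written.

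**3. What circular adjustment does to the estimate (MetS example).** The documents give no component means or correlations, so every input here is an assumption:

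- Five standard normal components, pairwise correlation 0.3.
- Cut-points at 0.25, 0.6, 0.7, 0.1 and 0.6 SD; MetS is three or more above the cut-point, which gives about 26% in controls.
- 261 versus 261, 600 simulated studies, logistic regression on group.
- The adjusted model adds two continuous components standing for waist and blood pressure.

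| Components that differ between groups | MetS, control v case | OR unadjusted | OR adjusted | Share with p<0.05, unadjusted → adjusted |
|---|---|---|---|---|
| all five, 0.25 SD | 26.2% v 38.9% | 1.80 | 1.37 | 86% → 22% |
| waist and blood pressure only, 0.4 SD | 26.3% v 33.9% | 1.44 | 0.66 | 49% → 35% |
| the other three only, 0.4 SD | 26.3% v 38.4% | 1.75 | 2.55 | 84% → 95% |

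Check on the first row: (0.389/0.611)/(0.262/0.738) = 1.79, in line with the fitted 1.80. In the second row the adjusted estimate lies on the wrong side of 1, so its 35% is not power for the hypothesised effect.

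**4. Sensitivity to the set-up.** At 261 versus 522, with loadings of 0.45 to 0.6 on a common factor, an age term, and MetS at 28% v 40% (equal 0.25 SD shifts), adding waist and both pressures moves the OR from 1.76 to 1.35 and power from 94% to 32%. With equal shifts of 0.15 and 0.35 SD the OR moves from 1.41 to 1.20 and from 2.22 to 1.52. A third set-up at 261 versus 522 (loading 0.53, control MetS about 32%) gives 1.78 to 1.38 and 96% to 38% under equal 0.25 SD shifts. Its two other patterns give 1.45 to 0.68 and 1.75 to 2.47. The three set-ups agree on the equal-shift result, and the two that tried other patterns agree that direction depends on which components differ.

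**The case against.** The strongest reply is that section 10.1 is the outcome-specific text and should prevail over a general sentence and a pooled list. On that reading MetS has no adjusted model, ASCVD and OSAS have none either, and 10.3 merely records how background variables are coded. This is a reasonable reading, and it means the error is conditional. It does not close the point. No precedence is stated, the section 10 sentence covers every outcome, 10.3 says the variables will be used as covariates, and the 10.1 wording for ASCVD and OSAS is open to the narrower reading.

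Three stronger inferences are tempting, and the documents do not support them:

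- **That the plan definitely adjusts outcomes for their own components.** It does so only if sections 10 and 10.3 override 10.1.
- **That the adjustment removes the effect or always pulls it to the null.** The equal-shift OR stays at about 1.4, and other patterns reverse or inflate it.
- **That the DM model has fewer than five events per term.** On the pilot rates, 261 × (0.085 + 0.099 + 0.181) ≈ 95 DM cases. Over the roughly 20 terms of 10.3 that is 4.8 each, but 10.1 names 12 items for (pre)DM, giving 95/12 ≈ 7.9, and preDM cases would add to a combined outcome.

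It is also fair to say that neck circumference and BMI are described as questionnaire inputs but are not separate terms in the printed OSAS equation. Age is. The OSAS overlap through those two measures is therefore by description, not by formula.

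**Conclusion.** The conflict between sections 10, 10.1 and 10.3 is real and stands on the text alone. The circularity is conditional on which section is followed. Where it occurs, the adjusted odds ratio no longer estimates the difference set out in section 2, and its bias has no fixed sign. The sizes given (OR about 1.8 to about 1.4, power 86% to 22% at 261 per group) hold for MetS under assumed correlations and equal shifts. No corresponding figure has been worked out for ASCVD or OSAS.

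The unadjusted comparisons are unaffected, and so is the sample size. The plainest self-adjustment is in 10.1 itself. The (pre)DM outcome is read from HbA1c, and a prior diagnosis of DM is a record of the same disease, yet it is listed as a covariate. This should be corrected before analysis, and it does not call the design into question.

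**What to change.** Reconcile the opening text of section 10 with 10.1 and 10.3, and state that the outcome-specific text governs. In 10.3, replace the pooled covariate designation with one covariate set per outcome and a general rule: a variable that defines an outcome, feeds its score or records an earlier diagnosis of it may not adjust that outcome. In practice:

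- **MetS:** either no adjusted model, as 10.1 says, or one without waist, blood pressure and hypertension diagnosis. State a decision on BMI and DM diagnosis, which sit close to the waist and glucose criteria.
- **ASCVD risk:** no chart inputs, including blood pressure.
- **OSAS risk:** none of the questionnaire's body-measurement inputs, including neck circumference and BMI. Say whether the exploration in 10.1 involves a model and, if so, with which variables.
- **(pre)DM:** the 10.1 list in place of the 10.3 list, without diagnosis of DM.

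Report the excluded variables descriptively by group. Apply the same sets in 10.2.

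The cost is SAP wording and fewer adjusted results for the composite outcomes. In particular, age and sex are inputs to the ASCVD and OSAS scores, so group differences in those scores will include any difference in age and sex, and the report should say so.

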### **11. ETHICAL CONSIDERATIONS**

### **11.1 Regulation statement**

The procedures set out in this study protocol are designed to ensure that the investigator abide by the principles of the good clinical practice guidelines of the European Community and the Declaration of Helsinki (19-10-2013) and in accordance with the Medical Research Involving Human Subjects Act (WMO) in the conduct, evaluation and documentation of this study. The study will also be carried out in keeping with local legal requirements.

### 11.2 Recruitment and consent

### Patients with periodontitis

Patients with periodontitis, referred to the department of Periodontology (ACTA), will receive an information letter about the study from their dental practitioner (of ACTA) at least 1 week before their visit to the periodontal clinic. The dental practitioner is informed by the researcher about the study and the recruitment of patients. During the appointment, patients will be asked by the dental practitioner whether they want to participate with the study. Patients can give consent. The terms of the consent and when it was obtained will be documented in the case record form. After the informed consent, the dental practitioner or researcher will fill in the questionnaires with the patients and use the finger stick analysis.

### Control subjects

Patients, visiting the dental clinic at ACTA for a regular dental checkup, will receive an information letter about the study from their dental practitioner (of ACTA) at least 1 week before their visit to the dental clinic. The dental practitioner is informed by the researcher about the study and the recruitment of patients. The dental practitioner performs the dental checkup. If the patient meets the inclusion criteria (see 8.3 Study procedures), then he/she will be asked by the dental practitioner (of ACTA) whether he/she wants to participate with the study. Patients can give consent. The terms of the consent and when it was obtained will be documented in the case record form. After the informed consent, the researcher will fill in the questionnaires with the patients and use the finger stick analysis.

Before being admitted to the clinical study, the patient must consent to participate after the nature, scope and possible consequences of the clinical study have been explained in an information letter understandable to him/her. In addition to the standard requirements that physicians are currently obliged to observe when providing information, all points on the information letter must be covered. The investigator will not undertake any investigation specifically required only for the clinical study until valid consent has been obtained. If the patient does not wish to know the result of the finger stick procedure, then he/she will not be included in the study.

# 11.3 Objection by minors or incapacitated subjects (if applicable)

NA

# 11.4 Benefits and risks assessment, group relatedness

- The extra burden for the patients and control subjects will be three questionnaires, measurement of length, body weight, waist and neck circumference, and a finger stick procedure.
- The risks associated with participation are negligible.
- Possible benefit of participation will be early detection of health risks such as (pre)DM, ASCVD, MetS, OSAS and possibly a referral for further diagnosis and/or treatment at the family physician.

### **11.5 Compensation for injury**

The sponsor/investigator has a liability insurance which is in accordance with article 7 of the WMO.

The sponsor (also) has an insurance which is in accordance with the legal requirements in the Netherlands (Article 7 WMO). This insurance provides cover for damage to research subjects through injury or death caused by the study.

- € 650.000,-- (i.e. six hundred and fifty thousand Euro) for death or injury for each subject who participates in the research;
- € 3.500.000,-- (i.e. three million five hundred thousand Euro) for death or injury for each research;
- € 7.500.000,-- (i.e. seven million five hundred thousand Euro) each year for all researches together.

All participants of this study will be informed about the insurance.

### **11.6 Incentives (if applicable)**

### Periodontitis as signal for an underlying disease

# 12. ADMINISTRATIVE ASPECTS, MONITORING AND PUBLICATION

# 12.1 Handling and storage of data and documents

All patient names will be kept secret. The patient number during the study will identify patients throughout documentation and evaluation. At inclusion, each study subject receives a research number. Each questionnaire is coded with a patient number and a research number. The research number corresponds to the blood sample of the finger stick procedure. The tubes with the obtained blood will be sent to the chemical laboratory of Labonovum B.V. with the coded research number written on it. This laboratory will report the results of the finger stick procedure for each research number. This way the laboratory will not have any insight to individual data of our patients.

The patients will be told that all study findings will be stored on computer and handled in strictest confidence. The investigator also agrees to allow these to be inspected on request. The investigator will maintain a personal list of patient numbers and patient names to enable records to be found at a later date. This personal list will be kept physically apart from the other data. The result of the finger stick procedure will be added to the medical history of the patient. Other documents and results, with individual patient numbers, will be kept for 15 years.

# 12.2 Monitoring and Quality Assurance

An independent monitor (quality officer) will monitor the study data according to Good Clinical Practice (GCP). During the selection of the study subjects, Informed Consents will be checked. In addition, Source Data Verification will be performed during onsite monitoring (checking whether the data of the Case Report Forms (questionnaires) are similar to the source data (patient status, lab results etc.). The intensity of this verification is related to the risk of the investigation. Data that also will be checked are the inclusion and exclusion criteria and the primary outcomes of the research. The monitor will also check whether all (S)AE's and SUSAR's are reported adequately within the time schedules as required by the law or regulations.

# 12.3 Amendments

Amendments are changes made to the research after a favourable opinion by the accredited METC has been given. The amendments will be submitted to the METC. All amendments will be notified to the METC that gave a favourable opinion. The starting date of the study will also be informed to the METC.

### NA

- A 'substantial amendment' is defined as an amendment to the terms of the METC application, or to the protocol or any other supporting documentation, that is likely to affect to a significant degree:
  - the safety or physical or mental integrity of the subjects of the trial;
  - the scientific value of the trial;
  - the conduct or management of the trial; or
  - the quality or safety of any intervention used in the trial.

All substantial amendments will be notified to the METC and to the competent authority.

Non-substantial amendments will not be notified to the accredited METC and the competent authority, but will be recorded and filed by the sponsor.

